## SYNOPSIS

### **Rationale for conducting the study:**

The operative treatment of idiopathic scoliosis typically involves a posterior correction with fixation by open surgery with simultaneous fusion of the operated levels. That type of surgery, although it leads to an almost anatomical correction, involves a long hospitalization time due to extensive tissue damage and pain. Recently, however, by using various regimes such as "ERAS" (enhanced recovery after surgery), including optimization of pain relief, inpatient stay times have been heavily reduced, and discharge as early as 1-2 days after surgery is now possible to achieve.

In recent years, there has been a development of minimally invasive techniques in spine surgery where tissue damage and blood loss are significantly minimized. It is of importance to scientifically investigate whether the use of minimally invasive techniques also in scoliosis surgery results in benefit for patients.

We need to investigate whether minimally invasive techniques are comparable to traditional open surgery in terms of reoperations, serious adverse events, infections, pain and radiologically healed fusion. One complexity of minimally invasive surgery (MIS) lies in the correct placement of implants in the deformed spine while preserving the tissue and not exposing the anatomical landmarks that usually guide for correct screw placement. It is why MIS practically entails the use of intraoperative 3D imaging or robotic assisted surgery (RAS) to improve screw placement accuracy.

The aim with this project is to evaluate whether MIS is non-inferior to the traditional open technique regarding reoperations, serious adverse events, infections, pain and radiologically healed fusion. At the same time, we want to compare the aforementioned techniques regarding inpatient stay, degree of correction, screw placement, neurophysiological incidences, blood loss, operation time, and patient related outcomes (PROMs).

As of yet, the majority of data in this area are based on retrospectively collected series, and some prospectively collected series, while randomized controlled trials are lacking.

**Study design:** Multicenter randomized controlled clinical trial.

**Study population:** Individuals with spinal deformity aged 10 through 25 years.

**Number of individuals:** 180

### **Inclusion criteria:**

- Written informed consent
- Idiopathic scoliosis
- Age between 10-25 years
- Posterior correction for scoliosis
- Major curve Cobb angle 75 degrees or less

### **Exclusion criteria:**

- Inability to give informed consent
- Other diagnosis of scoliosis than "idiopathic"

Clinical Study Protocol	Unique protocol ID	MISCOS
	Version No:	1.1
	Date:	2025-09-27

- Rigid curves that require posterior or three-column osteotomy/ies
- Previous surgery at the operated levels
- BMI > 35
- Psychological factors that make the patient unsuitable for inclusion in the study (e.g., substance abuse, developmental disability)

**Study inclusion period:**

Mid 2025-mid 2028

Clinical Study Protocol	Unique protocol ID	MISCOS
	Version No:	1.1
	Date:	2025-09-27

## LIST OF ABBREVIATIONS

Abbreviation	Explanation
RCT	Randomized Controlled Trial
MIS	Minimal Invasive Surgery
RAS	Robotic Assisted Surgery
3D	Three-dimensional
Swespine	Swedish Spine registry
CT	Computed Tomography
SRS-22r	Scoliosis Research Society 22 revised
EQ-5D-3L	EQ-5D three level
ODI	Oswestry Disability Index
EOSQ-24	Early Onset Scoliosis Questionnaire 24
SSI	Surgical Site Infection
CBCT	Cone Beam Computed Tomography

Clinical Study Protocol	Unique protocol ID	MISCOS
	Version No:	1.1
	Date:	2025-09-27

## 1. INTRODUCTION

### 1.1 Background

Idiopathic scoliosis is the most common type of spinal deformity with an overall prevalence of 1.9-3.0% and one of the most common reasons for extensive and complicated surgical treatments at youth. Beside the difficulties/challenges of treatment and the high cost for the healthcare system it can have a major impact on the quality of life of patients, both at the young age and later in life.

Proper recognition and treatment of idiopathic scoliosis helps to optimize patient outcomes. Treatment of idiopathic scoliosis depends on the curve size, curve progression and skeletal maturity. A Cobb curve angle greater than 45 degrees in skeletally immature individuals and 50 degrees in skeletally mature individuals are usual indications for surgery.

The operative treatment of idiopathic scoliosis typically involves a posterior correction with fixation by open surgery with simultaneous decortication of the operated levels. This type of surgery, although it leads to an almost anatomical correction, involves a long hospitalization time due to extensive tissue damage and pain. Recently, however, by using various regimes such as "ERAS" (early rehabilitation after scoliosis surgery) and by optimization of pain relief, reports of as short inpatient stay as 1-2 days exists.

In recent years, there has been an evolutionary development of minimally invasive techniques in spine surgery where tissue damage and blood loss are significantly minimized. It is therefore of great importance to scientifically investigate whether such a minimally invasive technique will mean even greater benefit for patients with an even shorter hospitalization and overall convalescence time.

At the same time, we need to investigate that the minimally invasive technique is not inferior compared to open surgery. One complexity of minimally invasive surgery (MIS) lies in the correct placement of implants in the deformed spine while preserving the tissue and not exposing the anatomical landmarks that usually guide for correct screw placement. This is why MIS practically entails the use of intraoperative 3D imaging and in some cases robotic assisted surgery (RAS) to achieve a high screw placement accuracy.

The primary aim with this project is to evaluate whether MIS is non-inferior to traditional open technique in terms of reoperations, serious complications, surgical site infections, pain and fusion rate in the long term. Moreover, we set out to compare the aforementioned techniques with regard to hospitalization time, accuracy of screw placement, neurophysiological incidences, blood loss, operation time, and patient related outcome measures (PROMs).

As of yet, the majority of data in this area are based on retrospectively collected series, and some prospectively collected series, while randomized controlled trials on spinal deformity are lacking. While MIS has rapidly developed in the field of degenerative spine surgery, it is important to investigate whether MIS in patients with idiopathic scoliosis could minimize inpatient stay and pain and at the same time not compromise other factors of a "successful" operation such as the degree of correction and fusion.

Clinical Study Protocol	Unique protocol ID	MISCOS
	Version No:	1.1
	Date:	2025-09-27

## 1.2 Ethical issues

We think it is important to evaluate the use of MIS in scoliosis patients because it may lead to better outcomes regarding reoperations, overall rehabilitation, infection rates, blood loss and inpatient stay. MIS techniques are already used widely in degenerative spine surgery as well as in spinal trauma and are well-established.

## 2 STUDY OBJECTIVES AND ENDPOINTS

### 2.1 Primary objective

Study design

This is a multi-center non-inferiority two arm randomized controlled trial. Results of MIS are expected to be non-inferior in terms of reoperations, serious complications, surgical site infection, pain and fusion rates compared to open surgery.

Definition of MIS:

Minimal invasive surgery (MIS) is here defined as a muscle salvage technique. Minimal invasive surgery is defined such that the posterior elements of the spine are not exposed and the spinal musculature is not detached from the posterior elements of the spine. That means that the erector spinae musculature is not detached from the spinous processes and the laminae, except for the exposure needed for the actual screw insertion. The surgeon is free to use either a long incision or multiple short incisions.

The arms consist of:

1. *Intervention group*

Patients operated with MIS: Minimal invasive surgery. The surgeon will be free to choose the method of screw placement. 3D-navigation, RAS, free hand technique or combinations of these may be used for screw placement. A long skin incision and subcutaneous multiple incisions are performed. The erector spinae musculature is not detached from the spinous processes and the laminae, except for the exposure needed for the actual screw insertion. Each screw is inserted through an incision in the musculature. The surgeon may choose to do decortication of all or some of the facet joints in the surgical area.

2. *Control group*

Patients operated with open surgery: Traditional open surgery. The surgeon will be free to choose the method of screw placement. 3D-navigation, RAS, free hand technique or combinations of these may be used for screw placement. A long skin and subcutaneous incision is performed. The posterior elements of the spine are exposed and the spinal musculature is detached from the posterior elements of the spine. The whole surgical area is exposed and all screws are inserted through this area. Separate incisions for screw placement in the musculature are not needed. The surgeon may choose to do decortication of all or some of the facet joints in the surgical area.

Clinical Study Protocol	Unique protocol ID	MISCOS
	Version No:	1.1
	Date:	2025-09-27

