## **Primary endpoint**

The primary endpoint is the assessment of a group of variables by the statistical method of “win odds”. The variables are in hierachic order:

- i. No reoperations at 2 years after surgery. A reoperation is defined as a secondary surgical procedure related to the index procedure and involving the spine at any level after the index procedure.
- ii. No serious complication related to the procedure. Serious complication is defined as a life-threatening complication or a complication related to substantial invalidity (like pneumothorax or spinal cord injury).
- iii. No early surgical site infection (SSI). Early SSI is defined as SSI with onset up to 12 weeks postoperatively.
- iv. No other infection related to the inpatient stay like pneumonia or urinary tract infection (UTI).
- v. Assessment of pain at 2 years f-u: The numeric rating scale (NRS) for back pain will be used measured on a scale from 0 (no pain) to 10 (worst possible pain). Data will be collected from Swespine or similar platforms.
- vi. Assessment of SRS-22r: The SRS-22r is a scoliosis specific questionnaire aiming to estimate quality of life in patients with scoliosis [1]. It contains 24 items divided into 5 domains covering function, pain, self-image, mental health, and satisfaction. An index value is calculated for each domain and a total index value is possible to calculate ranging from 1 (worst) to 5 (best). SRS-22r will be collected from Swespine or similar platforms at 2 years.
- vii. Radiologically healed fusion at 2 years f-u. A radiologically healed fusion is defined as bone bridging along the originally operated levels. A vertebral segment will be considered fused if one or both of the following conditions is satisfied:
  - a. Bone bridge over at least one facet joint
  - b. Bone bridge between the vertebral bodies

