## **2.2 Secondary objectives**

The following secondary objectives will be studied in comparisons between MIS and open operating procedures.

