### 6.2 Secondary variables

The secondary variables are listed below.

1. Inpatient stay in days.
2. The deformity correction rate will be assessed as Cobb-angle correction in a postoperative x-ray from the first standing radiograph compared to the last preoperative radiograph. The correction of the curve will be calculated according to the formula:  $(\text{preoperative Cobb angle} - \text{postoperative Cobb angle}) / (\text{preoperative Cobb angle}) \times 100\%$ .
3. Progression of Cobb angle in the operated levels at 2-years standing x-ray compared to the 3-month (first follow-up) x-ray. The progression of the curve will be calculated according to the formula:  $(\text{2-year Cobb angle} - \text{3-month Cobb angle}) / (\text{2-year Cobb angle}) \times 100\%$ .
4. Progression of secondary curve angles at 2-years standing x-ray compared to the 3-month (first follow-up) x-ray. The progression of the curve will be calculated according to the formula:  $(\text{2-year Cobb angle} - \text{3-month Cobb angle}) / (\text{2-year Cobb angle}) \times 100\%$ .
5. Perioperative blood loss (in mL).

Clinical Study Protocol	Unique protocol ID	MISCOS
	Version No:	1.1
	Date:	2025-09-27

6. Total procedure time (from incision to closure) as well as normalized to number of spinal levels from the upper to the lower instrumented vertebra (in min).
7. Accuracy at first attempt: Screws that are not placed and screws that are placed but repositioned after intraoperative verification are noted in the protocol. Accuracy of screw placement will be assessed as a score, calculated as the number of correctly placed screws divided by the total number of screws specified in the protocol (see Appendix 1 in the study protocol). The maximum score is 1, indicating perfect placement according to the preoperative plan. Screws graded Ia or Ib by the Heintel classification [2] are defined as correctly placed. Screws that are not inserted, or that require repositioning after intraoperative verification, will be recorded in the protocol and classified as NOT correctly placed.
8. Intraoperative neurophysiological monitoring. Neurophysiological monitoring is always performed as routine during spinal deformity surgery, with the exception of patients that are non-ambulatory. Motor evoked potential, sensory evoked potential and electromyography data will be collected to investigate any changes in neurophysiological parameters. Any deviations will be noted.

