9. Health economics: Total cost per patient during the first 2 years of the study including cost of possible re-admissions and reoperations related to index surgery. Data on costs on the individual level will be collected. These consist of costs for the inpatient and outpatient visits (including surgery, radiographs, navigation), analgesic and antibiotic treatments as well as possible re-admissions related to index surgery.
10. Patient reported outcome measures. Collected from Swespine or similar platforms after 1, 2, 5 and 10 years.
  - a. SRS-22r: The SRS-22r is a scoliosis specific questionnaire aiming to estimate quality of life in patients with scoliosis [1]. It contains 24 items divided into 5 domains covering function, pain, self-image, mental health, and satisfaction. An index value is calculated for each domain and a total index value is possible to calculate ranging from 1 (worst) to 5 (best).
  - b. EOSQ-24 is a proxy answered questionnaire and will be used in individuals up to the age of 15. It consists of 24 questions of daily function, pain, pulmonary function and mobility [3].
  - c. Oswestry Disability index (ODI) is used in individuals from 15 years and older. ODI is a back specific index measuring disability due to back pain [4]. It is the recommended instrument for studies concerning back pain. An index from 0-100 is calculated. An ODI of 0–20 indicate minimal disability, 21–40; moderate disability, 41–60; severe disability, 61–80; severely crippled, 81–100; bed-bound.
  - d. EQ-5D 3 level is a generic quality of life instrument and consists of five areas reflecting mobility, self-care, usual activities, pain/discomfort and anxiety/depression [5]. Response alternatives range from no problems to extreme problems. An index can be calculated and depending on baseline value set used the index runs between approximately -0.5 (worst possible health) to 1.0 (best possible health). The EQ-5D-3L will be used for health economic analyses. The EQ-VAS is part of the EQ-5D and registers the patient's self-rated health on a visual analogue scale (from 0 to 100; best).

Clinical Study Protocol	Unique protocol ID	MISCOS
	Version No:	1.1
	Date:	2025-09-27

- e. Postoperative pain relief assessed by NRS at discharge. Additionally, given and prescribed doses of analgesics that follow clinical routine protocols will be registered from the hospital files.

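### The objective claims non-inferior fusion, but the only non-inferiority test is a seven-tier win odds with fusion last, and no separate fusion comparison is listed

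*Protocol*

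**What the plan says.** The protocol states the aim three times as non-inferiority on named outcomes, each time including fusion:

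- Synopsis, rationale: "non-inferior to the traditional open technique regarding reoperations, serious adverse events, infections, pain and radiologically healed fusion".
- Section 1.1, as the primary aim: "non-inferior to traditional open technique in terms of reoperations, serious complications, surgical site infections, pain and fusion rate in the long term".
- Section 2.1: "expected to be non-inferior in terms of reoperations, serious complications, surgical site infection, pain and fusion rates compared to open surgery".

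Section 1.1 adds that MIS should not compromise other marks of a successful operation, "such as the degree of correction and fusion".

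The primary endpoint (section 2.1), the primary variables (6.1) and the analysis (7.2.1) define one win odds over seven ordered variables. The order is reoperation, serious complication, early surgical site infection, other infection, NRS back pain at 2 years, SRS-22r, and last "Radiologically healed fusion at 2 years f-u". The only non-inferiority limit in the document is a win odds of 0.60 (section 7.1).

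Section 2.2 opens with "The following secondary objectives will be studied in comparisons between MIS and open operating procedures" and section 6.2 with "The secondary variables are listed below". Neither list contains fusion. Deformity correction is there (6.2 item 2), and SRS-22r appears both as a primary tier and as a secondary variable (6.2 item 10a). Section 7.2.2 gives group comparisons for the secondary variables. Fusion is measured by the 2-year low-dose CT (5.8) and appears in the data collection table (8.1).

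**The concern.** A hierarchical win odds answers one question: whether a patient in one arm does better overall than a patient in the other under the chosen ordering. A pair is compared on fusion only if it is tied on all six earlier variables, two of which are scores with many levels. The composite can therefore be met whatever happens to fusion, while the stated objective invites readers to take a pass as non-inferior fusion.

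The protocol itself names fusion as something MIS must not compromise. As written, the trial could succeed on its primary criterion with a clearly lower MIS fusion rate, and no listed analysis compares fusion between the arms.

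**Working it through.** **Inputs from the protocol (7.1, 5.5).** 150 patients before dropout, 1:1, so 75 per arm; limit 0.60; true win odds 1.0; power 80%; independent outcomes. Component rates, score distributions and the confidence level are not given.

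**The plan's own figure.** At win odds 1 without ties, Var(log WO) = 8/(3n) for n per arm, so n = (8/3)(z_α + z_β)² / (ln 0.60)².

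- Two-sided 95% interval: n = 80.2, total 162; power at 75 per arm is 77.3%.
- One-sided 95% limit: n = 63.2, total 128.

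The stated 150 lies between the two and cannot be reproduced exactly. The point about fusion does not depend on it.

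**Assumptions for the simulation.** Reoperation 5%, serious complication 2%, early infection 3%, other infection 3%, open fusion 95%. Four score models: NRS gamma with mean 2 or mean 3, or with 45% or 60% zeros; SRS-22r total in steps of 1/22, mean 3.9–4.4, SD 0.3–0.6. Win odds with half of the ties to each side, U-statistic variance, delta method on the log scale, lower two-sided 95% limit compared with 0.60. There were 6,000 trials per cell for the base reading with equal arms and at 75% and 0% against 95%, and 3,000 for all other cells. Ranges run over the score models.

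**Base reading (any difference wins, complete scores, independent tiers).** 0.3–1.3% of pairs reach fusion.

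| MIS vs open fusion | Pass rate |
|---|---|
| Equal arms | 75–77% |
| 75% vs 95% | 75–77% |
| 0% vs 95% | 72–76% |

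**Other readings.**

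| Reading | 75% vs 95% | 5% vs 95% |
|---|---|---|
| SRS-22r win needs 0.2 | 70–75% | 34–68% |
| SRS-22r win needs 0.4 | 65–73% | 12–61% |
| SRS-22r 0.4 and NRS 2 | 63–73% | 5–33% |
| 10% missing both scores, as ties | 71–73% | 23–24% |
| 20% missing both scores, as ties | 66–67% | 2% |
| Non-fusion raises pain by 0.25 SD | 66–72% | 21–65% |
| Non-fusion adds 10 points of reoperation | 69% | 36–40% |

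With equal arms, the threshold and missing-score readings pass in 75–90%. Stronger or combined readings at 75% vs 95%:

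- pain link of 0.5 SD alone, 51–58%;
- pain 0.25 SD plus reoperation link, 59–66%;
- those two plus 20% missing, 52–59%;
- those two plus thresholds 0.4 and NRS 2, 53–57%;
- thresholds 0.4 and NRS 2 plus 20% missing, 55–63%.

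**Contrast with the first tier.** Reoperation at 10% vs 5% lowers the pass rate to 57–59%, and at 15% vs 5% to 36–39%. The composite responds to reoperation far more than to fusion.

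**What a separate comparison would show.** Half-width of the 95% interval for the risk difference = 1.96·√(p₁(1−p₁)/75 + p₂(1−p₂)/75).

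- 75% vs 95%: 1.96·√(0.0025 + 0.000633) = 11.0 points. By exact enumeration the interval excludes zero in about 95% of trials (Wald 95.5%, Newcombe 95.3%).
- 85% vs 95%: it excludes zero in 54–56%.
- 90% in both arms: 1.96·√(2·0.09/75) = 9.6 points.

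A formal fusion non-inferiority test with a 10-point margin (an assumed margin, one-sided 0.025) would have power of about 33%, 53% and 80% at true rates of 80%, 90% and 95%. The present sample size therefore supports an estimate of the fusion difference and does not reliably support a non-inferiority claim.

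**The case against.** - **An unseen SAP may report each component.** It may, and per-tier counts belong there. It would not change the objective, the single limit or the secondary list, which the protocol fixes.
- **The objective may be shorthand for the composite.** Section 2.1 goes on to define one win odds and never promises separate tests, and section 7.2.1 says the variables were chosen for clinical impact, so the low rank may be deliberate. This is a fair reading, and the order is not in dispute. But the aim is worded outcome by outcome in three places, and the composite cannot support it in that form.
- **The base reading minimises fusion.** It leaves almost no ties, whereas section 7.2.1 justifies win odds by the number of ties. It also gives 75–77% power and not 80%. In a check with two assumed score models, power exceeded 80% only with thresholds of NRS 2 and SRS-22r 0.4 (82–83%). There 17–25% of pairs reach fusion, and the 20-point deficit passes in 63–70%. With the confidence level unstated this does not settle the reading, since a one-sided limit gives about 85% without thresholds. It does mean that the full range must be read. An extreme deficit does pull the composite down under these readings.
- **Cobb progression in the operated levels is a listed secondary comparison.** It is related to fusion but does not measure it.
- **Precision is worse at lower fusion rates.** At 70% vs 50% the half-width is 15.3 points and power about 72%. This stands, and is one more reason to call the result an estimate.

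**Conclusion.** The concern holds. The protocol states non-inferiority on fusion but tests only a composite in which fusion is the last of seven tiers, and it lists no between-arm comparison of fusion alone. That mismatch is in the text and needs no assumptions. Its size does. A 20-point fusion deficit leaves the pass rate unchanged at 75–77% in the base reading, and still passes in 63–75% under a single threshold, missing-score or moderate-link reading and in 51–66% under the stronger or combined ones. The primary analysis remains valid for the composite. What is unsupported is the statement about fusion, so this should be fixed, but it does not invalidate the trial.

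**What to change.** 1. Reword the synopsis, section 1.1 and section 2.1 so that the win-odds result supports non-inferiority on the hierarchical composite (tiers i–vii) only.
2. Add 2-year radiological fusion to sections 2.2 and 6.2, with a between-arm risk difference and 95% confidence interval from the CT already scheduled. Describe it as an estimate and not as proof of non-inferiority. Because fusion is defined per segment, state how segments combine into a patient-level yes or no.
3. Only if statements on the other named outcomes are wanted, give the same separate estimate for each. At 75 per arm the approximate half-widths are 7.0 points for reoperation at 5%, 4.5 for serious complication at 2%, 5.5 for early infection at 3%, and 1.96·SD·√(2/75) = 0.64–0.80 for 2-year NRS back pain at an assumed SD of 2–2.5. With only about 1.5 to 2.3 expected events per arm for the two rarest outcomes, an interval suited to small counts is needed. Among the secondary variables NRS appears only as "Postoperative pain relief assessed by NRS at discharge", although SRS-22r (with its pain domain) and ODI are collected at 2 years.

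The order of the hierarchy need not change, and per-tier counts can be left to the SAP. The cost is a narrower claim and one further analysis (up to five with part 3), with no extra patients, visits or imaging. Under section 11 a changed secondary variable is a substantial amendment, so the Ethical Review Agency has to be informed and asked for its opinion or approval first.

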### 5.1 Minimal invasive scoliosis surgical correction- intervention group

Patients operated with MIS: Minimal invasive surgery. The surgeon will be free to choose the method of screw placement. 3D-navigation, RAS, free hand technique or combinations

Clinical Study Protocol	Unique protocol ID	MISCOS
	Version No:	1.1
	Date:	2025-09-27

of these may be used for screw placement. A long skin incision and subcutaneous multiple short incisions are performed. The erector spinae musculature is not detached from the spinous processes and the laminae, except for the exposure needed for the actual screw insertion. Each screw is inserted through an incision in the musculature. After placement of the screws, the positioning is checked with an intraoperative computed tomography. Misplaced screws may be repositioned or extracted. After implant placement, rods are bent to the desired shape and placed. Correction of the deformity and fixation is performed.

The surgeon may choose to do decortication of all or some of the facet joints in the surgical area. Decortication is performed by a navigated high-speed burr or other technique in a minimally invasive way. Finally, the wound/s is/are closed.

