## 5.2 Open scoliosis surgical correction- control group

Patients operated with open surgery: Traditional open surgery. The surgeon will be free to choose the method of screw placement. 3D-navigation, RAS, free hand technique or combinations of these may be used for screw placement. A long skin and subcutaneous incision is performed. The posterior elements of the spine are exposed and the spinal musculature is detached from the posterior elements of the spine. The whole surgical area is exposed and all screws are inserted through this area. Separate incisions for screw placement in the musculature are not needed. After placement of the screws, the positioning is checked with an intraoperative computed tomography. Misplaced screws may be repositioned or extracted. After implant placement, rods are bent to the desired shape and placed. Correction of the deformity and fixation is performed. The surgeon may choose to do decortication of all or some of the facet joints in the surgical area. The surgeon may choose to do decortication of the spinous processes and laminae in the surgical area. Decortication is performed by a high-speed burr or other technique. Finally, the wound is closed.

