## 5.4 Blinding

The study design does not allow blinding of the surgeons and other personnel in the operating theatre. However, the patient and other health-care personnel will be blinded and held up to two years postoperatively. Patient reported outcomes will be assessed without influence of the caregiver.

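### The protocol contradicts itself on the MIS skin incision; if multiple short incisions are used, scars can undo the stated two-year blinding and bias the self-reported tiers towards MIS

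*Protocol*

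**What the plan says.** **MIS, definition (section 2.1).** "The surgeon is free to use either a long incision or multiple short incisions". The sentence does not say whether skin or muscle is meant.

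**MIS, arm description (section 2.1, intervention group).** "A long skin incision and subcutaneous multiple incisions are performed". Section 5.1 has nearly the same sentence: "A long skin incision and subcutaneous multiple short incisions are performed". In both, the skin incision is single and long, and the multiple incisions lie beneath it.

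**MIS, closure (section 5.1).** "Finally, the wound/s is/are closed", which again leaves room for several wounds.

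**Open surgery (section 5.2).** "A long skin and subcutaneous incision is performed", and at the end "Finally, the wound is closed".

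**Blinding.** Section 5.4 says that "the patient and other health-care personnel will be blinded and held up to two years postoperatively". Section 3.1 also states postoperative blinding of patients and health-care personnel, with the surgeons as the exception among those involved in follow-up. Neither section describes a means of masking the scar or of checking the blind.

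**Primary endpoint (section 2.1).** The win-odds hierarchy has seven tiers. Tier v (back pain NRS) and tier vi (SRS-22r) are reported by the patient at 2 years.

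**The concern.** Under the definition, a MIS patient may have several short scars. Under the arm descriptions, every MIS patient has one long scar, like the controls. The two statements cannot both govern, and the blinding claim depends on which one does.

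Nothing in the open arm can produce several short scars, so a patient with that pattern who knows the two techniques can infer MIS. So can the staff who inspect the wound at 2-4 weeks and record SSI outcomes there (Table 1). Patients who know that they had the newer, less invasive operation may report less pain and better SRS-22r scores. In a non-inferiority comparison such an expectation effect works in favour of MIS and can hide a real disadvantage.

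The operation form in Appendix 1 has no field for the incision pattern, so that form would not show how many patients were affected.

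**Working it through.** **1. The passages side by side**

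| Place | Skin incision | Wounds closed |
|---|---|---|
| 2.1, definition of MIS | long, or multiple short | not stated |
| 2.1, MIS arm | one long | not stated |
| 5.1, MIS arm | one long | one or several |
| 5.2, open arm | one long | one |

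The definition and the closing words of 5.1 permit a pattern that the MIS arm descriptions do not, and that the open arm cannot show.

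**2. How many pairs reach the self-reported tiers**

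The protocol has no figure for this and no event rates, so the rates below are assumptions. If a binary event has rate q in both arms, a pair ties on it with probability q² + (1−q)². Independence, which section 7.1 assumes, lets the four tiers be multiplied.

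| Assumed rates: reoperation, serious complication, early SSI, other infection | Pairs tied on tiers i-iv |
|---|---|
| 3%, 1%, 1%, 1% | 0.89 |
| 5%, 2%, 2%, 2% | 0.80 |
| 10%, 3%, 5%, 5% | 0.63 |

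A separate simulation of the full hierarchy counted pairs actually decided by NRS or SRS-22r. It assumed NRS mean 2.5 and SD 2.3, SRS-22r mean 4.0 and SD 0.5, and fusion in 90%. The share was 88% at rates of 3/1/1/1%, 75% at 6/2/3/3% and 56% at 12/5/6/6%.

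**3. Effect on the type I error**

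Inputs from section 7.1: margin 0.60, and 180 patients less 20% dropout, which is 144, or 72 per arm. Assumptions: one-sided 2.5% level, 80% of pairs reaching the self-reported tiers, and an expectation effect of 0.2 SD in MIS patients with short incisions only.

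- Win probability at the margin: 0.60/1.60 = 0.375. It is taken to be the same on the event tiers and the self-reported tiers.
- On the self-reported tiers, Φ(d/√2) = 0.375 gives a true shift d = −0.4506 SD.
- Win probability of an affected MIS patient: 0.8·Φ((−0.4506 + 0.2)/√2) + 0.2·0.375 = 0.4187.
- If a share s of MIS patients is affected: W = s·0.4187 + (1−s)·0.375, and win odds = W/(1−W).
- Standard error of the log win odds, without ties: 4·√(145/(12·72·72)) = 0.193.
- Type I error: Φ(ln(win odds/0.60)/0.193 − 1.96).

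| Share of MIS patients with short incisions | W | Apparent win odds | Type I error |
|---|---|---|---|
| 0% | 0.375 | 0.60 | 2.5% |
| 25% | 0.386 | 0.63 | about 4% |
| 50% | 0.397 | 0.66 | about 7% |
| 100% | 0.419 | 0.72 | about 16% |

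**The case against.** **The procedural text points to similar scars.** Both passages that describe what is done to MIS patients state a long skin incision. If they govern, the arms look alike and this route to unblinding closes. That stands: the concern is conditional. A reader might infer that the blind is bound to fail, but the protocol does not support this, because short incisions are at most an option.

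**The definition may refer to muscle incisions.** This is possible, but the sentence is unqualified, and the plural wounds in 5.1 point to skin. Wording that can be read both ways still has to be settled.

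**A large error rate applies only in the extreme case.** A reader might take 16% as the trial's type I error. It requires every MIS patient to have short incisions, infer the allocation and report better scores. A MIS patient with a long scar learns nothing from it, and nor does a control patient, since MIS may look the same. The objection is right that the share with short incisions drives the result, which is why the table varies it.

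**Self-report deciding most pairs is not a documented fact.** It held under every set of rates tried above, but it remains an inference. In the simulation's assumptions, tiers i-iv would decide half of the pairs if all four event rates were about 9%.

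**There are partial safeguards.** Section 3.1 provides blinded review of postoperative imaging and record data, and 3.1 and 5.4 keep caregivers from influencing patient reports. These protect other parts of the endpoint. They do not stop patients from drawing conclusions from their own scars.

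**Conclusion.** The contradiction is real. The definition of MIS in 2.1 and the plural wounds in 5.1 allow a skin incision pattern that the MIS arm descriptions in 2.1 and 5.1 do not. If that pattern is used, it conflicts with the blinding stated in 3.1 and 5.4 and can bias tiers v and vi towards MIS.

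The direction is clear, but the size cannot be read from the protocol. The 4%, 7% and 16% rest on assumed event rates, an assumed 0.2 SD effect, an assumed confidence level and a normal approximation, and they scale with the share of MIS patients who have short incisions. If that share is zero, there is no inflation by this route.

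The point warrants a protocol change because it concerns the definition of the intervention and the blinding statement, which a statistical analysis plan would not settle.

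**What to change.** 1. Reconcile the definition of MIS with the arm descriptions in 2.1 and 5.1, including the closure wording in 5.1, and say whether skin or muscle incisions are meant. This review does not say which incision is right.
2. If visibly different skin incision patterns remain possible, limit the two-year blinding claim in 3.1 and 5.4 accordingly.
3. In that case, add a field for the skin incision pattern to the operation form in Appendix 1.
4. Also ask patients which operation they think they had, preferably early (for example at the 3-month visit) as well as at 2 years. A guess made only at 2 years is mixed with outcome, because a patient who did well may guess MIS for that reason.
5. Do not use the win odds by incision pattern to judge the bias. The surgeon chooses the pattern, it varies only within MIS, and it is open to confounding by surgeon, centre and curve. If reported at all, label it descriptive.

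The cost is wording, one operative field and one questionnaire item. The 3-month and 2-year visits already exist, so no extra visit is needed.
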